1.1 Synopsis

Protocol Title:

A Phase IIIb, Open-label, Multi-center Study to Evaluate the Immunogenicity and Safety of a Booster Dose and Describe the Immune Persistence of MenACYW Conjugate Vaccine with 5- and/or 10-year Booster Doses in Children and Adolescents who had been Primed with MenACYW Conjugate Vaccine as Toddlers

Short Title:

Study on an Investigational Quadrivalent Meningococcal Conjugate Vaccine (MenACYW Conjugate Vaccine) Administered as a 5- and/or 10-year Booster Dose in Children and Adolescents Vaccinated 5 or 10 Years Earlier as Toddlers

Rationale:

The purpose of Amendment 1.0 is to add a study arm in order to describe the immunogenicity and safety of a booster dose and the persistence of a priming dose of MenACYW conjugate vaccine (MenQuadfi®) in adolescents who had been vaccinated with MenACYW conjugate vaccine approximately 10 years earlier as toddlers as part of the MET51 study. It is also to increase the study duration in the initial study arm to describe the immunogenicity and safety of a second booster dose (as adolescents approximately 5 years after the first booster dose) and the persistence of a first booster dose of MenACYW conjugate vaccine in adolescents who had been primed with MenACYW conjugate vaccine as toddlers as part of the MET51 study and had received a first booster dose as children approximately 5 years after the priming dose.

Objectives and Endpoints:

Objectives	Endpoints

Primary
 
 To demonstrate the vaccine seroresponse sufficiency of meningococcal serogroups A, C, W, and Y after the administration of a booster dose of MenACYW conjugate vaccine in children who received 1 dose of MenACYW conjugate vaccine approximately 5 years earlier as toddlers (Group 1) 	
 Vaccine seroresponse¹ against meningococcal serogroups A, C, W, and Y measured by serum bactericidal assay using human complement (hSBA) assessed at Visit (V)1 (baseline) and at V2 (30 days after the administration of a booster dose of MenACYW conjugate vaccine) (Group 1) 
¹ Seroresponse is defined as the proportions of participants with an hSBA pre-vaccination titer < 1:8 who achieved a post-vaccination titer ≥ 1:16 or participants with a pre-vaccination titer ≥ 1:8 who

	achieved a post-vaccination titer at least 4-fold greater than the pre-vaccination titer
Key Secondary	

Immunogenicity
 
 To describe the antibody persistence of meningococcal serogroups A, C, W, and Y in children who received MenACYW conjugate vaccine approximately 5 years earlier as toddlers (Groups 1 and 2) To describe the antibody persistence of meningococcal serogroups A, C, W, and Y in adolescents who received MenACYW conjugate vaccine approximately 10 years earlier as toddlers (Group 2) To describe the antibody persistence of meningococcal serogroups A, C, W, and Y in adolescents who received a booster as children approximately 5 years after the primary dose of MenACYW conjugate vaccine as toddlers (Group 1) To describe the antibody responses to meningococcal serogroups A, C, W, and Y before and 30 days after the administration of a booster dose of MenACYW conjugate vaccine in children who received MenACYW conjugate vaccine approximately 5 years earlier as toddlers (Group 1) To describe the antibody responses to meningococcal serogroups A, C, W, and Y before and 30 days after the administration of a booster dose of MenACYW conjugate vaccine in adolescents who received MenACYW conjugate vaccine approximately 10 years earlier as toddlers (Group 2) 	
Immunogenicity
 
 Antibody titers² against meningococcal serogroups A, C, W, and Y measured by hSBA and serum bactericidal assay using baby rabbit complement (rSBA) at V1 for Group 1 and Group 2 Antibody titers² against meningococcal serogroups A, C, W, and Y measured by hSBA and rSBA at V2 (Group 2) Antibody titers² against meningococcal serogroups A, C, W, and Y measured by hSBA and rSBA at V3 (Group 1) Antibody titers² against meningococcal serogroups A, C, W, and Y measured by hSBA and rSBA at V1 (baseline) and V2 (30 days after the administration of a booster dose of MenACYW conjugate vaccine) (Group 1) Antibody titers² against meningococcal serogroups A, C, W, and Y measured by hSBA and rSBA at V2 and V3 (30 days after the administration of a booster dose of MenACYW conjugate vaccine) (Group 2)


 • To describe the antibody responses to meningococcal serogroups A, C, W, and Y before and 30 days after the administration of a booster dose of MenACYW conjugate vaccine in adolescents who received a booster as children approximately 5 years after the primary dose of MenACYW conjugate vaccine as toddlers (Group 1) • To describe the antibody responses to tetanus toxoid before and 30 days after the administration of each booster dose of MenACYW conjugate vaccine in children (Group 1) and adolescents (Group 2) who received MenACYW conjugate vaccine approximately 5 or 10 years earlier as toddlers and in children who received a booster approximately 5 years after the primary dose of MenACYW conjugate vaccine as toddlers (Group 1) • To describe the antibody responses to meningococcal serogroup C before and 30 days after the administration of a booster dose of MenACYW conjugate vaccine 
 ○ In children who received MenACYW conjugate vaccine approximately 5 years earlier as meningococcal vaccine naïve toddlers (MET51 Group 1) (Group 1) ○ In children who received MenACYW conjugate vaccine approximately 5 years earlier as meningococcal C (MenC)-primed toddlers (MET51 Group 3) (Group 1) ○ In adolescents who received MenACYW conjugate vaccine approximately 10 years earlier as meningococcal vaccine naïve toddlers (MET51 Group 1) (Group 2) 	
 • Antibody titers² against meningococcal serogroups A, C, W, and Y measured by hSBA and rSBA at V3 and V4 (30 days after the administration of a booster dose of MenACYW conjugate vaccine) (Group 1) • Antibody concentrations against tetanus toxoid at V1 (baseline) and V2 (30 days after the administration of a 5-year booster dose of MenACYW conjugate vaccine) (Group 1) • Antibody concentrations against tetanus toxoid at V3 and V4 (30 days after administration of the second booster dose of MenACYW conjugate vaccine) (Group 1) • Antibody concentrations against tetanus toxoid at V2 and V3 (30 days after administration of a 10-year booster dose of MenACYW conjugate vaccine) (Group 2) • Antibody titers² against meningococcal serogroup C measured by hSBA and rSBA at V1 (baseline) and V2 (30 days after the administration of a 5-year booster dose of MenACYW conjugate vaccine) (Group 1) • Antibody titers² against meningococcal serogroup C measured by hSBA and rSBA at V3 and V4 (30 days after the administration of the second booster dose of MenACYW conjugate vaccine) (Group 1) • Antibody titers² against meningococcal serogroup C measured by hSBA and rSBA at V2 and V3 (30 days after the administration of a 10-year booster dose of MenACYW conjugate vaccine) (Group 2)
--	---

 ○ In adolescents who received MenACYW conjugate vaccine approximately 10 years earlier as MenC-primed toddlers (MET51 Group 3) (Group 2) ○ In adolescents who received MenACYW conjugate vaccine booster as children approximately 5 years after receiving the primary dose of MenACYW conjugate vaccine as meningococcal vaccine naïve toddlers (MET51 Group 1) (Group 1) ○ In adolescents who received MenACYW conjugate vaccine booster as children approximately 5 years after receiving the primary dose of MenACYW conjugate vaccine as MenC-primed toddlers (MET51 Group 3) (Group 1) 	
² Results will be expressed as vaccine seroresponse, seorprotection, and GMTs

Safety
 
To describe the safety profile of a booster dose of MenACYW conjugate vaccine:
 
 ● in children who received MenACYW conjugate vaccine approximately 5 years earlier as toddlers in MET51 (Group 1) ● in adolescents who received MenACYW conjugate vaccine approximately 10 years earlier as toddlers in MET51 (Group 2) ● in adolescents who received a booster dose as children approximately 5 years after the primary dose of MenACYW conjugate vaccine as toddlers (Group 1) 	
Safety
 
The safety profile will be evaluated within 30 days (+14 days) after vaccination. The following endpoints will be used for the evaluation of safety:
 
 ● Unsolicited systemic adverse events (AEs) reported within 30 minutes after vaccination ● Solicited (prelisted in the participant’s diary card [DC] and [electronic] case report book [CRB]) injection site and systemic reactions starting any time from the day of vaccination through 7 days after vaccination ● Unsolicited (recorded in a DC) non-serious AEs reported within 30 days after vaccination(s) ● Serious adverse events (SAEs) (including adverse events of special interest [AESIs]) reported throughout the study

Overall Design

This is a Phase IIIb, open-label, multi-center study to evaluate the immunogenicity and safety of a booster dose and describe the immune persistence of a priming dose of MenACYW conjugate vaccine in children and adolescents in Finland, Germany, Spain, and Hungary who had been vaccinated with MenACYW conjugate vaccine approximately 5 or 10 years earlier as toddlers as part of the MET51 study, and to describe the immunogenicity and safety of a second booster dose and the persistence of a first booster dose of MenACYW conjugate vaccine in adolescents who had been vaccinated with MenACYW conjugate vaccine approximately 5 years earlier as children.

Participants who were vaccinated with MenACYW conjugate vaccine approximately 5 years earlier at 12 to 23 months of age in study MET51 will be eligible for enrollment in study MEQ00073. Eligible participants will be stratified to 1 of 2 groups based on country and MenC status (primed [Hungary, Spain] or naïve [Finland, Germany]). Participants in Group 1 will receive a first booster dose of MenACYW conjugate vaccine on D01 (V1) (at child age approximately 5 years post priming dose as toddlers in study MET51) and a second booster dose of MenACYW conjugate vaccine at Year 5 of study MEQ00073 (at adolescent age approximately 5 years post booster dose as children in study MEQ00073). Participants in Group 2 will receive a single booster dose of MenACYW conjugate vaccine at Year 5 of study MEQ00073 (approximately 10 years post priming dose as toddlers in study MET51).

All participants will provide blood samples (BL) for antibody persistence and immunogenicity assessments at V1 (pre-vaccination for Group 1 [D01]); participants in Group 1 will also provide a BL at V2 (D31 +14 days), 30 days post-first booster vaccination. Participants in both groups will provide a BL at Year 5 (V3 for Group 1, Visit 2 for Group 2) for antibody persistence and immunogenicity assessments prior to receiving a booster vaccination of MenACYW conjugate vaccine, and another BL 30 days post-booster vaccination (V4 for Group 1, V3 for Group 2).

Solicited AE information will be collected for 7 days after each vaccination; unsolicited AE information will be collected for 30 days (+14 days) after each vaccination. Serious AE information (including AESIs) will be collected throughout the study period.

Type of design	open-label, multi-center and multi-country
Phase	IIIb
Control method	uncontrolled
Study population	Healthy children approximately 6 to 7 years of age at the time of enrollment who were vaccinated with MenACYW conjugate vaccine approximately 5 years earlier as toddlers (12 to 23 months of age) in the MET51 study (Group 1 [naïve] and Group 3 [MenC-primed])
Countries	Finland, Germany, Hungary, Spain
Level and method of blinding	open-label
Study intervention assignment method	randomly selected

Disclosure Statement:

This is an open-label study.

Number of Participants:

All available and eligible participants, who participated in and completed the MET51 study and received a single dose of MenACYW conjugate vaccine as a part of the study, can be enrolled. Participants from MET51 will be invited to participate in MEQ00073, with around 250 participants each in Group 1 and in Group 2 (maximum estimate).

Intervention Groups and Duration:

Participants in Group 1 will receive a first booster dose of MenACYW conjugate vaccine at D01 and a second booster dose of MenACYW conjugate vaccine at Year 5 of study MEQ00073. Participants in Group 2 will receive a single booster dose of MenACYW conjugate vaccine at Year 5 of study MEQ00073.

The duration of each participant’s participation will be approximately 5.5 years.

[figure not shown]
Data Monitoring Committee:

Not applicable

1.2 Schema

The graphical design of study MEQ00073 is presented in [Figure 1.1](#).

Figure 1.1 – Graphical study design

AE: adverse event; D: day; N/A: not applicable; SAE: serious AE; TC: telephone call; V: visit; Y: year

*The TC at D09 and the D31 visit (V2, Group 1) are applicable only to Group 1 participants

† This TC is applicable to both groups, and will be done approximately 8 days after V3 (Group 1) / V2 (Group 2)

1.3 Schedule of Activities (SoA)

Visits procedures are detailed in the Operating Guidelines.

Table 1.1: Schedule of activities, Group 1

Phase IIIb Study, 4 Visits (V), 6 Telephone Calls (TC), 2 Vaccinations, 4 Blood Samples (BLs), 5.5 Years Duration per Participant

Visit/Contact	Collection of information in the CRF	Visit 1 (V1)	TC1	Visit 2 (V2)	TC2	TC3	TC4	TC5	Visit 3 (V3)	TC6	Visit 4 (V4)
Trial timelines (days)		Day 01 (D01)	Day 09 (D09) V1 + 8d	Day 31 (D31) V1 + 30d	Year 1 V1 + 12m	Year 2 V1 + 24m	Year 3 V1 + 36m	Year 4 V1 + 48m	Year 5 V1 + 60m	Year 5 Day 09 V3 + 8d	Year 5 Day 31 V3 + 30d
Time windows (days)		-	+2d	+14d	+14d	+14d	+14d	+14d	+14d	+2d	+14d
Informed consent form (ICF)/Assent form (AF) (As applicable and if required by country regulation, a new AF will be signed by the adolescent aged participant at V3)	X	X							X		
Inclusion/exclusion criteria*	X	X									
Collection of demographic data	X	X									
Collection of medical history	X	X									
Collection of vaccination history	X	X									
Physical examination		X							X		

Visit/Contact	Collection of information in the CRF	Visit 1 (V1)	TC1	Visit 2 (V2)	TC2	TC3	TC4	TC5	Visit 3 (V3)	TC6	Visit 4 (V4)
Trial timelines (days)		Day 01 (D01)	Day 09 (D09) V1 + 8d	Day 31 (D31) V1 + 30d	Year 1 V1 + 12m	Year 2 V1 + 24m	Year 3 V1 + 36m	Year 4 V1 + 48m	Year 5 V1 + 60m	Year 5 Day 09 V3 + 8d	Year 5 Day 31 V3 + 30d
Time windows (days)		-	+2d	+14d	+14d	+14d	+14d	+14d	+14d	+2d	+14d
Urine pregnancy test (if applicable)									X		
Review warnings and precautions and / or contraindications for vaccination	X	X							X		
Review of temporary contraindications for blood sampling [†]	X	X		X					X		X
Blood sample (BL), 5 mL [‡]		BL1		BL2					BL3		BL4
Randomization/stratification of participant number	X	X									
Study Vaccination		X							X		
Immediate surveillance post vaccination (30 minutes)	X	X							X		
Diary card (DC) provided		DC1		DC for safety					DC2		
Telephone call (TC)			X§		X	X	X	X		X§	
Recording of solicited injection site & systemic reactions	X	Day 01 to Day 08							V3 to 7d post-V3		

Visit/Contact	Collection of information in the CRF	Visit 1 (V1)	TC1	Visit 2 (V2)	TC2	TC3	TC4	TC5	Visit 3 (V3)	TC6	Visit 4 (V4)
Trial timelines (days)		Day 01 (D01)	Day 09 (D09) V1 + 8d	Day 31 (D31) V1 + 30d	Year 1 V1 + 12m	Year 2 V1 + 24m	Year 3 V1 + 36m	Year 4 V1 + 48m	Year 5 V1 + 60m	Year 5 Day 09 V3 + 8d	Year 5 Day 31 V3 + 30d
Time windows (days)		-	+2d	+14d	+14d	+14d	+14d	+14d	+14d	+2d	+14d
Recording of unsolicited AEs (to be collected up to 30d after vaccination)	X			X							X
Reporting of SAEs (including AESIs**)	X	To be reported throughout the study period									
DC collected				DC1							DC2
Collection of reportable concomitant medications	X	X		X					X		X
Termination record	X										X

AE: adverse event; AESI: adverse event of special interest; AF: assent form; AR: adverse reaction; BL: blood sample; CRF: case report form; D, d: day(s); DC: diary card; ICF: informed consent form; m: month(s); mL: milliliter; SAE: serious adverse event; TC: telephone call; V: visit

* Temperature to be measured by oral, rectal, or axillary route (axillary preferred) using a certified standard digital thermometer and recorded in the source document.

† Should a participant receive oral or injectable antibiotic therapy within 3 days prior to each blood draw, the Investigator will postpone that blood draw until it has been 3 days since the participant last received oral or injectable antibiotic therapy. Postponement is still to be within the timeframe for blood draw (30 to 44 days after vaccination at D01). If postponement will result in the sample collection falling outside of the appropriate timeframe, the blood sample should be collected without postponement, and it should be documented appropriately that the sample was taken less than 3 days after stopping antibiotic treatment.

‡ Blood samples at V1 (BL1) and V3 (BL3) are to be drawn before administration of the vaccine.

§ This call is to be made 8 to 10 days after the vaccination visit. If the contact date (+2 days) falls on a weekend or holiday, the TC may be made on the following business day. During this TC, the staff will find out whether the participant experienced any SAEs, including AESIs, not yet reported, and are to remind the participant's parent/legally acceptable representative (LAR) to continue using the DC up to the next visit, to bring the DC to the study center at the next visit, and to confirm the date and time of the next visit.

** AESIs will be collected throughout the trial as SAEs to ensure that the events are communicated to the Sponsor in an expedited manner and followed up until the end of the follow-up period or resolution, as per the assigned causality.

Table 1.2: Schedule of activities, Group 2

Phase IIIb Study, 3 Visits (V), 5 Telephone Calls (TC), 1 Vaccination, 3 Blood Samples (BLs), 5.5 Years Duration per Participant

Visit/Contact	Collection of information in the CRF	Visit 1 (V1)	TC1	TC2	TC3	TC4	Visit 2 (V2)	TC5	Visit 3 (V3)
Trial timelines (days)		Day 01 (D01)	Year 1 V1 + 12m	Year 2 V1 + 24m	Year 3 V1 + 36m	Year 4 V1 + 48m	Year 5 V1 + 60m	Year 5 Day 09 V2 + 8d	Year 5 Day 31 V2 + 30d
Time windows (days)		-	+14d	+14d	+14d	+14d	+14d	+2d	+14d
Informed consent form (ICF)/Assent form (AF) (As applicable and if required by country regulation, a new AF will be signed by the adolescent aged participant at V3)	X	X					X		
Inclusion/exclusion criteria*	X	X							
Collection of demographic data	X	X							
Collection of medical history	X	X					X		
Collection of vaccination history	X	X							
Physical examination		X							
Urine pregnancy test (if applicable)							X		
Review warnings and precautions and / or contraindications for vaccination	X						X		

Visit/Contact	Collection of information in the CRF	Visit 1 (V1)	TC1	TC2	TC3	TC4	Visit 2 (V2)	TC5	Visit 3 (V3)
Trial timelines (days)		Day 01 (D01)	Year 1 V1 + 12m	Year 2 V1 + 24m	Year 3 V1 + 36m	Year 4 V1 + 48m	Year 5 V1 + 60m	Year 5 Day 09 V2 + 8d	Year 5 Day 31 V2 + 30d
Time windows (days)		-	+14d	+14d	+14d	+14d	+14d	+2d	+14d
Review of temporary contraindications for blood sampling†	X	X					X		X
Blood sample (BL), 5 mL		BL1					BL2‡		BL3
Randomization/stratification of participant number	X	X							
Study Vaccination							X		
Immediate surveillance post vaccination (30 minutes)	X						X		
Diary card (DC) provided		DC for safety					DC1		
Telephone call (TC)			X	X	X	X		X§	
Recording of solicited injection site & systemic reactions	X						V2 to 7d post-V2		
Recording of unsolicited AEs (to be collected up to 30d after vaccination)	X								X
Reporting of SAEs (including AESIs**)	X		To be reported throughout the study period						
DC collected									DC1

Visit/Contact	Collection of information in the CRF	Visit 1 (V1)	TC1	TC2	TC3	TC4	Visit 2 (V2)	TC5	Visit 3 (V3)
Trial timelines (days)		Day 01 (D01)	Year 1 V1 + 12m	Year 2 V1 + 24m	Year 3 V1 + 36m	Year 4 V1 + 48m	Year 5 V1 + 60m	Year 5 Day 09 V2 + 8d	Year 5 Day 31 V2 + 30d
Time windows (days)		-	+14d	+14d	+14d	+14d	+14d	+2d	+14d
Collection of reportable concomitant medications	X	X					X		X
Termination record	X								X

AE: adverse event; AESI: adverse event of special interest; AF: assent form; AR: adverse reaction; BL: blood sample; CRF: case report form; D, d: day(s); DC: diary card; ICF: informed consent form; m: month(s); mL: milliliter; SAE: serious adverse event; TC: telephone call; V: visit

* Temperature to be measured by oral, rectal, or axillary route (axillary preferred) using a certified standard digital thermometer and recorded in the source document.

† Should a participant receive oral or injectable antibiotic therapy within 3 days prior to each blood draw, the Investigator will postpone that blood draw until it has been 3 days since the participant last received oral or injectable antibiotic therapy. Postponement is still to be within the timeframe for blood draw (30 to 44 days after vaccination at D01). If postponement will result in the sample collection falling outside of the appropriate timeframe, the blood sample should be collected without postponement, and it should be documented appropriately that the sample was taken less than 3 days after stopping antibiotic treatment.

‡ Blood sample at V2 (BL2) is to be drawn before administration of the vaccine.

§ This call is to be made 8 to 10 days after the vaccination visit. If the contact date (+2 days) falls on a weekend or holiday, the TC may be made on the following business day. During this TC, the staff will find out whether the participant experienced any SAEs, including AESIs, not yet reported, and are to remind the participant's parent/legally acceptable representative (LAR) to continue using the DC up to the next visit, to bring the DC to the study center at the next visit, and to confirm the date and time of the next visit.

** AESIs will be collected throughout the trial as SAEs to ensure that the events are communicated to the Sponsor in an expedited manner and followed up until the end of the follow-up period or resolution, as per the assigned causality. Before the first booster vaccination at V2, only SAEs related to study procedures are to be collected for Group 2.

2 Introduction

The MenACYW conjugate vaccine (MenQuadfi[®]) was designed for the immunization of individuals of all ages (children as young as 6 weeks of age, adolescents, and adults including those 56 years of age and older) against invasive meningococcal disease (IMD). The purpose of the vaccine is to provide broad coverage against circulating meningococcal strains from serogroups A, C, W, and Y.

The clinical development program targets licensure of the MenACYW conjugate vaccine in many countries in North America, Europe, Latin America, Africa, the Middle East, and Asia Pacific. It has been licensed for active immunization of individuals from 2 years of age in the United States (US) since April 2020, and for active immunization of individuals from 12 months of age in the European Union (EU) since November 2020, and some other countries under the brand name of MenQuadfi[®].

MenACYW conjugate vaccine has been evaluated in over 7500 participants (infants, toddlers, adolescents, and adults, including those > 56 years of age) in completed Phase II and Phase III studies. In these studies, MenACYW conjugate vaccine was found to be well tolerated and did not reveal any apparent safety concerns. Phase III studies are ongoing to investigate the vaccine in infants from 6 weeks of age.

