7.1 Discontinuation of Study Intervention

7.1.1 Temporary Contraindications for Vaccination

Should a participant experience one of the conditions listed below, the Investigator will postpone further vaccination until the condition is resolved. Postponement must still be within the timeframe for vaccination indicated in the SoA.

- TCI01: Febrile illness (temperature $\geq 38.0^{\circ}\text{C}$ [$\geq 100.4^{\circ}\text{F}$]) or moderate or severe acute illness / infection on the day of vaccination, according to Investigator judgment
- TCI02: Receipt of any vaccine in the 4 weeks preceding the trial vaccination or planned receipt of any vaccine in the 4 weeks following trial vaccination except for influenza vaccination, which may be received at least 2 weeks before or after study vaccines. This exception includes monovalent pandemic influenza vaccines and multivalent influenza vaccines
- TCI03: Receipt of oral or injectable antibiotic therapy within 72 hours prior to the blood draw
- TCI04: Receipt of immune globulins, blood or blood-derived products in the past 3 months

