	
least 1 of the following relevant protocol deviations will be excluded from the PPAS1 or PPAS2 as applicable.
 
• Participant did not meet all protocol-specified inclusion criteria or met at least one of the protocol-specified exclusion criteria• Participant did not receive vaccine• Participant received a vaccine other than MenACYW conjugate vaccine• Preparation and/or administration of vaccine was not done as per-protocol• Participant did not receive vaccine in the proper time window• Participant did not provide post-dose serology sample in the proper time window or a post-dose serology sample was not drawn• Participant received a protocol-prohibited Category 2 or Category 3 therapy/medication/vaccine• Participant’s serology sample did not produce a valid test result (ie, results for all meningococcal antigens are missing)• Participant had other protocol deviations that affected the participant’s immune response, as determined by the clinical team before locking the database• Participant’s serology sample did not produce a valid test result (ie, results for all meningococcal antigens are missing)• Participant had other protocol deviations that affected the participant’s immune response, as determined by the clinical team before locking the database
--	--

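### The antibiotic-postponement footnote measures every blood draw against a D01 vaccination window that fits one of seven draws and contradicts the Year 5 visit windows

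*Protocol*

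**What the plan says.** The rule is a footnote to the row on temporary contraindications for blood sampling in Protocol Section 1.3, Tables 1.1 (Group 1) and 1.2 (Group 2). SAP Tables 1.2 and 1.3 repeat it. It has three parts.

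- Scope: "Should a participant receive oral or injectable antibiotic therapy within 3 days prior to each blood draw", the investigator postpones that draw until three days have passed since the last antibiotic dose.
- Limit: "Postponement is still to be within the timeframe for blood draw (30 to 44 days after vaccination at D01".
- Fallback: "If postponement will result in the sample collection falling outside of the appropriate timeframe, the blood sample should be collected without postponement", with the exposure documented.

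Other current text bears on the same draws.

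- The column headings of the schedule time the Year 5 post-dose draws from each group's own Year 5 dose: "Year 5 Day 31 V3 + 30d" for Group 1 and "Year 5 Day 31 V2 + 30d" for Group 2, each with a +14 day window. The Year 5 dosing visit is at V1 + 60 months, also +14 days.
- Group 2 has no dose at D01: "Participants in Group 2 will receive a single booster dose of MenACYW conjugate vaccine at Year 5 of study MEQ00073".
- Protocol 7.1.2 gives the same postponement rule and fallback without mentioning D01.
- Protocol 7.1.1 lists, among the reasons to postpone vaccination within the schedule's vaccination window, "TCI03: Receipt of oral or injectable antibiotic therapy within 72 hours prior to the blood draw".
- Protocol 6.5 makes systemic antibiotics in the 72 hours before a draw a Category 3 medication, because they may disturb the bioassay. Section 9.3 then excludes from the PPAS on this ground: "Participant received a protocol-prohibited Category 2 or Category 3 therapy/medication/vaccine".

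**The concern.** The footnote claims to govern all draws but supplies a timeframe that describes only one. At Year 5 a postponed sample can never lie 30 to 44 days after D01. A reader who takes the parenthesis at its word therefore reaches the fallback every time, even when a short delay would keep the sample inside the visit window. Protocol Section 8 calls adherence to the schedule of activities essential, and the footnote is part of that schedule, so sites cannot simply be expected to ignore it.

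What is at stake is the quality and completeness of the Year 5 serology, which Amendment 1.0 was written to obtain. A sample drawn on antibiotics removes the participant from PPAS2. The possibly affected titer remains in FAS2 or, for the pre-dose sample, in FAS4. The SAP uses FAS4 for the 10-year persistence estimate in Group 2 and the 5-year post-booster persistence estimate in Group 1, and FAS4 carries no antibiotic exclusion.

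**Working it through.** **Where the stated window comes from.** Group 1 V2 is V1 + 30 days with a +14 day window, and V1 is D01. So 30 to 30 + 14 = 44 days after D01. The footnote's figure is reproduced exactly, for Group 1 BL2.

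**Each scheduled draw against that window.** There are 4 draws in Group 1 and 3 in Group 2, so 7 in all. Sixty months is taken as about 1,826 days. The Year 5 dosing visit then falls at days 1,826 to 1,826 + 14 = 1,840. The post-dose draw falls between 1,826 + 30 = 1,856 and 1,840 + 44 = 1,884.

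| Draw | Timing in the schedule | Days after D01 | Inside 30 to 44? |
|---|---|---|---|
| Group 1 BL1 | V1, before the dose | 0 | No |
| Group 1 BL2 | V1 + 30d, +14d | 30 to 44 | Yes |
| Group 1 BL3 | V1 + 60m, +14d, before the dose | 1,826 to 1,840 | No |
| Group 1 BL4 | V3 + 30d, +14d | 1,856 to 1,884 | No |
| Group 2 BL1 | V1, no dose | 0 | No; no D01 dose to count from |
| Group 2 BL2 | V1 + 60m, +14d, before the dose | 1,826 to 1,840 | No; no D01 dose to count from |
| Group 2 BL3 | V2 + 30d, +14d | 1,856 to 1,884 | No; no D01 dose to count from |

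The window fits 1 draw of 7. The earliest Year 5 draw misses it by 1,826 − 44 = 1,782 days. The two V1 draws matter less, because exclusion criterion E16 already covers antibiotics before the first draw. The draws at issue are the four at Year 5.

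**Which texts conflict.** For Group 1 BL4 and Group 2 BL3, the footnote's limit conflicts with the column headings, which allow 30 to 44 days after the Year 5 dose, and with 7.1.2, which has no D01 anchor. For Group 1 BL3 and Group 2 BL2, it also conflicts with TCI03. The literal fallback takes the sample at once, while TCI03 postpones the vaccination planned for that same visit.

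**Possible size.** The documents give no rate of antibiotic use. Assume a proportion q of participants has had systemic antibiotics within 72 hours of a given draw, with q from 1% to 3%, and take the planned maximum of 250 per group.

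- Per draw: 250 × 0.01 = 2.5 and 250 × 0.03 = 7.5, so about 3 to 8 per group.
- Over both Year 5 draws, if exposures are independent: 250 × (1 − 0.99²) = 5.0 and 250 × (1 − 0.97²) = 14.8, or 2.0% to 5.9% of 250.

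The SAP adds FAS2 when attrition from FAS2 to PPAS2 exceeds 10%, which is 25 of 250. Losses in this range would not trigger it on their own.

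These are upper bounds. They assume full retention to Year 5, literal compliance with the footnote at every site, and that every exposed draw could otherwise have been moved.

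**The case against.** A reader might infer that the plan directs sites to draw on antibiotics at Year 5 and so to lose participants from PPAS2. The documents do not support that. The footnote's first instruction is to postpone. Section 7.1.2 repeats the rule with no D01 anchor, the schedule rows give usable Year 5 windows, and TCI03 postpones the Year 5 dose. In Group 2 there is no D01 dose to count from, so a sensible site would turn to the column headings. Sites also have Operating Guidelines that are not available here. This part of the objection stands: the plan contradicts itself and does not issue a single wrong instruction.

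It also stands that the loss cannot be put down to the footnote alone. The antibiotic rate is assumed, and 250 is an enrolment maximum before five years of attrition. A continuing antibiotic course can use up much of a 14-day window. Section 7.1.2 itself accepts some exposed draws, so some would occur even with a correct window.

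The consequences are bounded as well. Year 5 immunogenicity is descriptive. Persistence uses FAS4, so no one is lost from it. Protocol 9.4.1 plans both PPAS and FAS for all immunogenicity analyses, although the SAP makes FAS2 conditional on attrition above 10%.

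What does not stand is that other text settles the matter. Section 7.1.2 refers to the draw's timeframe without defining it, and the footnote is the text that does define it, wrongly for Year 5. TCI03 concerns vaccination and does nothing for the two post-dose draws. Keeping an exposed sample in FAS4 avoids a loss but retains a suspect titer.

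**Conclusion.** The point holds as a minor internal contradiction in an operational rule. The timeframe in the four footnotes is right for Group 1 BL2, cannot be met at any of the four Year 5 draws, and refers in Group 2 to a dose that is not given. Applied literally, it replaces postponement with an immediate draw at Year 5, against the schedule's own windows, Section 7.1.2 and, before the dose, TCI03.

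The exposure is confined to secondary descriptive Year 5 results on PPAS2, FAS2 and FAS4. The primary endpoint rests on Group 1 V1 and V2: BL2 has the correct window and BL1 is covered by E16.

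The size cannot be derived from the documents. The 3 to 8 participants per group per draw depend on the assumed 1% to 3% exposure, 250 per group and literal compliance. They should be read as a ceiling and not as an expected loss.

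**What to change.** In the footnotes to Protocol Tables 1.1 and 1.2 and SAP Tables 1.2 and 1.3, reconcile the parenthesis with the windows already in the column headings and with Section 7.1.2, so that the timeframe refers to each draw's own visit window. Section 7.1.2 could point to those rows, so that the term is defined in one place. Separately, reconcile the fallback with TCI03 in Section 7.1.1 for the Year 5 pre-dose draws. The sponsor's clinical team must decide how the two rules fit together.

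The cost is a wording change in four footnotes, plus a cross-reference. No visit, sample or procedure is added. The change is useful only if sites have it before Year 5 sampling begins.
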